# Baseline (Week 0)

Subjects must continue to meet all inclusionary and exclusionary criteria at this visit

- Study clinician will administer Baseline Scales
- Vital signs (blood pressure, pulse, height, weight, temperature)
- Subjects will receive study medication as indicated by a blinded randomization schedule

# Weekly Visits (Weeks 1 through 12)

Weekly study visits will have a visit window of +/- 2 days to facilitate scheduling.

During these visits:

- The study clinician will ask the parents/guardians questions about their child's symptoms of bipolar disorder
- The study clinician will also ask if the participant is having any side effects and if they have taken any other medications since the last visit
- Blood pressure, pulse, height, weight, and temperature will be obtained
- At the last visit, subjects will undergo repeat cognitive evaluation. Subjects who are dropping from the study will also undergo repeat cognitive evaluation if they have been exposed to the study medication for at least two weeks.

# Study Discontinuation

Subjects may drop at any time due to patient preference, physician decision, need for psychiatric hospitalization, or a poor response to treatment. Poor response to treatment will be measured by a CGI-bipolar score that is 2 points higher (more severe) than baseline for 2 weeks in a row or a YMRS score that is 30% higher than baseline for 2 weeks in a row, which may lead to drop from the study as determined by the clinician. Subjects with individual YMRS item scores of 8 on Item #8 (Content), or scores greater than 6 on Disruptive-Aggressive Behavior for 2 weeks in a row may be dropped from the study. Initial and emergent suicidality will be assessed weekly through administration of the Columbia Suicide Severity Rating Scale (C-SSRS). Subjects scoring 4 or higher will be dropped from the study. In addition, drop from study will occur at clinician discretion for worsening of clinical course, non-compliance with treatment or inability to tolerate study treatment.

Subjects will receive three months of optional pro bono clinical care visits (one monthly appointment over three months' time) at the completion of the study (or if they are required to discontinue for the above reasons) in which they will be seen by study staff. No research data will be collected at these follow-up visits. The three months of follow-up care are a courtesy that is offered to help find long-term care. Subjects will receive referrals to treaters in their communities.

Subjects who fail to return medication for two consecutive visits, fail to keep study appointments, or are non-compliant (less than 70% compliance for two weeks or longer) may be dropped from the study. These study subjects will be given a referral to treaters in their area.

If a subject becomes pregnant or is found to be abusing substances during the study, he or she will be discontinued from the study and given a referral as well. Since our target subject population is children 5-12 years of age, we do not anticipate that any participant will be at risk for pregnancy. However, a urine pregnancy test will be completed for female subjects ages 11-12 at screening. A physical exam, Tanner's staging, and parent report are collected at the screening as well visit to ascertain pubertal status. For subsequent study visits, pregnancy status is determined by verbal query of parent and/or subject or additional urine tests if needed.

If a subject would like us to forward their clinical history to his/her primary care physician, or a new clinician, we will forward any pertinent information. If a subject who has come from the clinic of the investigator happens to drop out of the study, he or she will return to his or her treating physician.

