Eligible subjects will be required to come into the office for weekly visits for the 12week study. During this time subjects will receive treatment with inositol, omega-3 fatty acids, or both. Subjects will be randomized to treatment arms in a double-blind fashion. Although every effort will be made to encourage subjects to keep regularly scheduled appointments, in the event that a subject is unable to come into the office within a reasonable timeframe of a scheduled study visit, and the treating research clinician feels that subject safety will not be jeopardized by doing so, the clinician may conduct the visit with the subject over the phone. During the phone visit, the clinician will complete all study scales for that visit. This will ensure that each subject will be continuously monitored by the clinician throughout the course of the study despite unforeseen scheduling circumstances. However, neither the study evaluation visit, nor the baseline visit, nor the final study visit may be conducted over the phone. Additionally, phone visits may not occur for two consecutive visits.

Vital signs (blood pressure, pulse, weight, height, temperature) will be measured at every visit. Those subjects who terminate study participation before the completion of the study will be asked to complete all tasks scheduled to take place on the final study visit at the time of study discontinuation.

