# 9. DATA ANALYSIS

# A. Statistical Analysis

90 subjects will be randomized (1:1:1) into one of three treatment groups: inositol, omega-3 fatty acids, or inositol plus omega-3 fatty acids. Subjects will be block-randomized to ensure equal age and gender distribution between groups. Because this is a randomized trial following subjects over a short period of time missing data are not expected to impact our analyses such that standard statistical analyses will be employed. Changes in ratings of mania within and between study groups over time will be tested with repeated measures analysis of covariance using the statistical software package STATA. All analyses will be intention to treat (ITT) with the last observation carried forward for subjects that do not complete the trial or are dropped from the study according to the exit criteria described earlier.

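### Children removed before week 12 are rated only at exit and carried forward as ITT, while research data are barred at the follow-up visits that some of them are offered

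*Combined protocol and SAP*

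**What the plan says.** **Exit rules.** In section 7, Study Discontinuation, the response to a child doing badly on treatment is removal from the study. One trigger is "a YMRS score that is 30% higher than baseline for 2 weeks in a row, which may lead to drop from the study". A CGI-bipolar score 2 points worse than baseline over the same span is another. More broadly, "drop from study will occur at clinician discretion for worsening of clinical course, non-compliance with treatment or inability to tolerate study treatment". A later paragraph adds that children who "are non-compliant (less than 70% compliance for two weeks or longer) may be dropped from the study", and groups them with those who miss appointments or do not return medication.

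**Last rating.** Section 7 states that children who leave early are "asked to complete all tasks scheduled to take place on the final study visit at the time of study discontinuation". Table 1 places YMRS and CDRS among those tasks. Nothing schedules a rating after that point.

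**Contact after exit.** Study Discontinuation offers three optional monthly appointments with study staff to children who complete "(or if they are required to discontinue for the above reasons)". It then says: "No research data will be collected at these follow-up visits". For the low-compliance, missed-appointment and unreturned-medication group, the text says only: "These study subjects will be given a referral to treaters in their area".

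**Analysis.** Section 9.A says "All analyses will be intention to treat (ITT) with the last observation carried forward", and names children removed under the exit criteria among those to whom this applies. The same paragraph expects missing data to have no effect on the results. No dropout rate and no sensitivity analysis are given.

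**The concern.** The plan makes stopping study treatment the same event as leaving the study. A child removed at week 4 therefore has no observed week-12 YMRS or CDRS, and both are primary measures in section 8 (Efficacy Measures). The exit rating stands in for them.

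These values are not missing at random in any simple sense. Several exit rules act on the YMRS or the CGI itself, so the carried value is often a rating chosen because it was high. What happens next is unknown: the child may settle, may improve on other treatment, or may worsen further. Hypothesis 2 predicts that the combination outperforms each single agent. If so, exits for poor response should be rarer in the combination arm, and unequal exit is the condition under which LOCF distorts the comparison between arms.

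The gap is partly avoidable. For at least some removed children, study staff have already offered to see them around week 12, and the protocol says that nothing is to be recorded. Outcomes that are not collected cannot be recovered at the analysis stage.

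**Working it through.** The plan has no figure of its own on this point to reproduce. The power figures in section 9.C do not enter the argument.

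**1. Who has no week-12 rating, and who is offered visits**

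| Reason for exit | Rating after exit | Follow-up offer |
|---|---|---|
| Poor response, worsening, intolerance | none scheduled | three optional monthly visits, no research data |
| Non-compliance at clinician discretion (named before the offer) | none scheduled | appears to be covered by the offer |
| Under 70% compliance, missed appointments, unreturned medication (named after the offer) | none scheduled | only a referral mentioned |

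The second and third rows overlap, so the text does not settle what a non-compliant child is offered.

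**2. How far a value can be carried.** The poor-response rule needs two consecutive weekly ratings, so it can first act at about week 2. The carry is then up to 12 − 2 = 10 weeks. At baseline scores of 20 to 40, a 30% rise means an exit score at least 0.30 × 20 = 6 to 0.30 × 40 = 12 points above baseline.

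**3. Whether an offered visit falls near week 12.** Take a month as 4.345 weeks and visits at t + 4.345, t + 8.69 and t + 13.035 for removal at week t.
- Removed at week 2: about weeks 6.3, 10.7 and 15.0.
- Removed at week 4: about weeks 8.3, 12.7 and 17.0.
- Removed at week 8: about weeks 12.3, 16.7 and 21.0.
- Removed at weeks 9, 10 and 11: first visit at about weeks 13.3, 14.3 and 15.3.

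For removal at weeks 2 to 8, one optional visit falls within about two weeks of week 12. For weeks 9 to 11, the first visit comes after the endpoint.

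**4. How many children.** The plan assumes no rate. The only related figure is the pilot in section 1: 4 of 20 left for ineffectiveness, 4/20 = 20%. If that applied here (an assumption, since the pilot was an 8-week open-label study of omega-3 alone), 0.20 × 90 = 18 children, or 6 per arm, would have carried values.

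**5. Possible shift in the contrast.** Let p be the proportion removed in an arm and g the mean of the carried value minus the true week-12 value.

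Shift on a week-12 contrast = p_B × g_B − p_A × g_A. With a common g this is (p_B − p_A) × g.

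Assumed inputs, none of them from the documents: p_A = 0.10, p_B = 0.30, and g from 3 to 8 points.
- g = 3: 0.20 × 3 = 0.6 points.
- g = 5: 0.20 × 5 = 1.0 point.
- g = 8: 0.20 × 8 = 1.6 points.
- Equal p and equal g: 0.

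**6. If the 12 follow-ups are averaged.** Section 9.A plans repeated-measures ANCOVA and does not say whether the contrast is at week 12 or over all visits. For removal at week 4, with drift building linearly over weeks 5 to 12, the summed drift is (1 + 2 + … + 8)/8 = 4.5 visit-equivalents. Averaged over 12 visits this is 4.5/12 = 0.375 of the full drift.
- Shift: 0.20 × 0.375 × 3 = 0.2 to 0.20 × 0.375 × 8 = 0.6 points.
- If the full drift occurs at once: 0.20 × (8/12) × 3 = 0.4 to 0.20 × (8/12) × 8 = 1.1 points.

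**7. Direction.** If removed children improve after exit, g is positive and LOCF makes the arm with more exits look worse than it was at week 12. If they worsen further, the sign reverses. The documents do not determine which applies.

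**The case against.** The strongest reply is that the plan has defined a coherent outcome, namely the status at the last study visit. Children who leave are assessed at exit, and that assessment is what the analysis uses. Ratings taken later, possibly on other treatment, answer a different question and could narrow a real difference between arms. The follow-up visits are a courtesy intended to help families find care, so adding research ratings changes their purpose and needs consent. This stands in part. It means that ratings on other treatment must be identified and the question being answered must be stated. It does not make an exit value carried for up to 10 weeks an observed endpoint, and the plan offers no check on how much depends on it.

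Three stronger readings are tempting, and the documents do not support them.

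- A reader might infer that every removed child, including those below 70% compliance, is seen monthly by study staff. The visits are optional. The paragraph with the 70% criterion mentions only a referral, and children who leave by their own preference are not clearly among those required to discontinue.
- A reader might set 0.6 to 1.6 points against the 5-point difference in section 9.C and conclude that LOCF distorts 12 to 32% of it. The removal rates and drift are assumed. The range applies only to a pure week-12 contrast, whereas section 9.C computes power for a design with 12 follow-ups.
- A reader might infer that collecting ratings after exit repairs the gap. Retrieval would be partial and possibly selective, and some ratings would reflect other treatment. It reduces reliance on LOCF but does not remove the missing-data problem.

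**Conclusion.** The point holds as a design weakness that should be corrected at low cost. Children removed before week 12 have no observed week-12 YMRS or CDRS, the exit rating is carried forward and called ITT, and research data are barred at visits clearly offered to those required to stop for poor response, worsening or intolerance. For the low-compliance, missed-appointment and unreturned-medication group, access to those visits is unclear.

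The size of any bias is unknown because the plan states no dropout rate. The illustrative 0.6 to 1.6 YMRS points rests on a difference in removal of 20 percentage points, a common drift of 3 to 8 points and a week-12 contrast. It falls to about 0.2 to 1.1 points under the averaging cases above, and to zero if removal and drift are equal across arms.

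The number of children affected cannot be derived either. The exit rules are mostly discretionary, and they are worded differently in Study Discontinuation, in section 9 (Safety) and in section 12 (Protection Against Risk). Those passages must be reconciled.

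**What to change.** **Study Discontinuation.** Separate stopping study treatment from leaving the study. Remove the bar on research data. Ask consenting families of removed children for one YMRS and CDRS rating as near week 12 as possible, at the nearest follow-up visit where one is held and otherwise at a single rating visit. Reconcile the paragraphs on what non-compliant children are offered. The removal criteria do not change.

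**Section 9.A.** Include the retrieved ratings in the ITT analysis. Use a likelihood-based mixed model for repeated measures on all observed ratings, so that children without a retrieved rating contribute what was observed without a carried value. State whether the contrast is at week 12 or over all visits. Keep LOCF as a sensitivity analysis. Report removals by arm and reason, and which ratings were taken on other treatment.

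**Cost.** Consent and protocol wording, and a little rater time per removed child. For many exits at weeks 2 to 8 an offered visit already falls near week 12. For later exits, and for families given only a referral, a separate contact is needed. Retrieval will be partial and possibly selective, and some ratings will reflect other treatment. The mixed model still assumes that, given the observed ratings, missingness carries no further information, which cannot be verified.

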# Audio Recordings

For quality control purposes, the rating scales completed during the visits will be recorded. These recordings will be used to monitor quality control and inter-rater reliability in this study by the PI. Each recording will be coded with patient initials and number to maintain confidentiality. These recordings will be stored in a password-protected database.

# Data Collection

Data will be collected using StudyTRAX. StudyTRAX is an electronic data capture system that streamlines data collection and management and ensures data integrity. StudyTRAX software allows researchers to design and implement study surveys for collected, story, retrieving, and manipulating data electronically.

Participants and/or research staff will enter survey responses into electronic assessment forms, using computer terminals at the research site. The responses will then be transmitted securely via an encrypted connection and stored in a secured database. Electronic data capture obviates the need for subsequent data entry by staff, thus minimizing human error. However, it is still possible that rating scales will be collected in paper form in the case that StudyTRAX is not working or unavailable.

# 8. ASSESSMENTS (see Table 1)

# 1. K-SADS-E (Epidemiologic Version)

- We will collect information for psychiatric diagnoses in children with study relevant modules of the KSADS-E (Epidemiologic Version) (Orvaschel, 2004).
- This is a widely used, semistructured, diagnostic interview with established psychometric properties. It can be effectively administered by clinicians in 45 to 90 minutes, although more complex cases may require additional time.
- For all children, psychiatric data will be collected from the mother, or primary caretaker. All children and primary caregivers will be seen in direct clinical interview with the treating clinician.
- The mania and depression modules will be administered prior to the baseline visit by the clinician to ensure entry criteria are met.

# 2. Background Information

- Prior to administering the cognitive measures at baseline, the child and a parent (or his/her legal guardian) will be asked a series of short questions about the child's background to establish socioeconomic status. Information gathered includes: sex, age, race/ethnicity, intactness of parents, home environment, financially responsible providers (using an SES scale, see below), history of head injury, trauma, and academic functioning. This will be entered on both the standard departmental form, and the study-specific form ("Background Information/KSADS face page").
- The Four Factor Index of Social Status (SES) (Hollingshead, 1975) will be used as a general measure of social advantage or disadvantage.

# 3. Child Behavior Checklist-Parent Form (CBCL)

The CBCL (Achenbach, 2000; Achenbach, 2001) is a standardized assessment of child behavior problems and social competence. Due to its extensive use and available norms, it provides us with an effective method of comparing our sample with others in the literature.

- The CBCL records, in standardized format, the behavioral problems and competencies of children aged 4 to 18, as reported by their parents or parentsurrogates.
- The CBCL is scored on the recently revised social competence and behavior problem scales of the Child Behavior Profile. A T-score above 70 is considered to be a clinically meaningful indicator of childhood psychopathology.
- Administered at beginning of study to characterize the groups and ensure their similarity.

# 4. Social Adjustment Inventory for Children and Adolescents (SAICA)

- The SAICA (John, 1987) is a semi-structured interview of the child or parent that measures social functioning in children 6 to 18 years old.
- Content areas assessed include activities, peer relations, family relations, and academic performance. A total score is then calculated as the arithmetic mean of all global rating scores.
- We will administer this scale at beginning of study and endpoint to assess the impact of treatment on social functioning.

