# 6. SUBJECT SELECTION CRITERIA

# A. Inclusion Criteria:

- 1. Male or female subjects, 5-12 years of age.
- Subjects must have a DSM-IV diagnosis of a bipolar spectrum disorder (type I, II, or Not Otherwise Specified (NOS)), and currently displaying mixed, manic, or hypomanic symptoms (without psychotic features) according to the DSM-IV based on clinical assessment and confirmed with structured diagnostic interview (Schedule of Affective Disorders and Schizophrenia for School-Age Children Epidemiological Version (K-SADS-E)) (Orvaschel, 1994).
- 3. Subjects and their legal representative must have a level of understanding sufficient to communicate intelligently with the investigator and study coordinator, and to cooperate with all tests and examinations required by the protocol.
- 4. Subjects and their legal representative must be considered reliable.
- 5. Each subject and his/her authorized legal representative must understand the

nature of the study. The subject's authorized legal representative must sign an informed consent document and the subject must sign an informed assent document.

- 6. Subjects must have an initial score on the YMRS total score of at least 20.
- 7. Subject must be able to swallow pills.
- 8. Subjects with ADHD and ODD will be allowed to participate in the study provided that the impairment associated with these disorders is of mild or moderate severity (not severe) and milder in severity relative to the impairment of the bipolar disorder, according to clinician evaluation. Subjects with comorbid anxiety disorders will be allowed to participate provided that the impairment associated with the anxiety is of minimal severity, according to clinician evaluation. Subjects with comorbid cD will be excluded.

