# Screening Visit

Before any participant can start the study, the study clinician will discuss the details of the study with the participant and his/her parent/guardian. Before starting the screening process, the study clinician will obtain informed consent from the parent or guardian and assent from the child subject. Assent will be obtained, in writing, from each child age 7-12 years who, in the opinion of the Investigator, is capable of providing assent based on their age, maturity, and psychological state. When assent is not obtained, the Investigator will document his/her rationale in the research records.

After the consent/assent form is signed, we will do the following:

- Review medical and health questions with the participant and their parents/guardians. (For example, "Does your child have a history of any medical conditions such as diabetes or hypertension?")
- Conduct a brief demographic interview. This interview will be used to estimate socioeconomic status, as well as collect information about any educational accommodations, and past head injuries and trauma.
- Obtain psychiatric history and administer YMRS, the CDRS, the HAM-D, the C-SSRS, and the K-SADS-E mania and depression modules to determine that subject meets the diagnostic criteria of a current DSM-IV bipolar spectrum disorder (mixed, manic, or hypomanic) and has an YMRS score of ≥ 20 and < 40.

All exclusionary and inclusionary criteria will be reviewed. Appropriate patients will undergo:

- An assessment battery (CBCL, SAICA, FES)
- Cognitive evaluation [IQ and cognitive function (subtests of WISC-IV, WPPSI-III, or KBIT-2)]

- Select WPPSI-III subtests will be used in the place of the WISC-IV processing speed subtest for children younger than 6 years.
- The KBIT-2 will be used in the place of the WISC-IV to assess IQ in children younger than 6 years.
- Physical exam
- Tanner staging exam (clinician-administered to parent or subject, clinician exam with subject, or the option to refuse)
- Vital Signs (blood pressure, pulse, height, weight, temperature)

The above may take place over two visits over the course of three weeks, if necessary. All are to be completed prior to the Baseline Visit. Any subjects requiring medication washout must be tapered off this medication prior to Baseline Visit as indicated in the washout section. Patients who do not meet all the criteria for enrollment after these assessments will be discontinued.

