# 8. Neuropsychological Tests/Cognitive Evaluation

IQ Testing: At study beginning, subjects will complete a brief cognitive screen. The scales we will use meet the demand for quick reliable measures of intelligence in clinical, educational and research settings. These tests will provide estimates of verbal and nonverbal ability respectively, as well as the direct measure of Full Scale IQ. This portion of the cognitive evaluation will take

approximately 30 minutes to complete. In the unlikely event that a subject's estimated IQ is below 70, the subject will not be eligible to participate in the study. Depending upon the subject's age, the cognitive screen will consist of:

- **Subjects age 5:** Verbal Knowledge, Riddles, and Matrices subtests of the Kaufman Brief Intelligence Test, Second Edition (KBIT-2)(Kaufman & Kaufman, 2004)
- Subjects ages 6-12: Vocabulary and Matrices subtests of the Wechsler Abbreviated Scale of Intelligence (WASI)(Wechsler, 2003)
- Cognitive Functioning Testing: At screening and endpoint, to assess the impact of treatment on cognition, we will assess basic intellectual and cognitive functions purported to be deficient in patients with bipolar disorder. Cognitive deficits that have been observed in bipolar disorder may reflect dysfunction in the frontal subcortical circuits that support aspects of attention, executive functions processing speed, memory and learning (Bearden, 2001). The neuropsychological battery we have developed to assess these functions includes both published clinical measures with large, normative samples and experimental measures with strong empirical evidence of validity. This neuropsychological battery, which has been used widely in clinical trials and family studies in our office, has been well tolerated. The testing will take approximately 25 minutes to complete. The ageappropriate testing will include:
  - Subjects age 5: Symbol Search and Coding subtests of the Wechsler Preschool and Primary Scale of Intelligence (WPPSI-III) (Wechsler & Sattler, 2002) to measure processing speed
  - Subjects ages 6-12: Digit Span and Coding subtests from the Wechsler Intelligence Scale for Children-Fourth Edition (WISC-IV) (Wechsler, 2003) to measure working memory and processing speed

The working memory scale will be omitted for subjects who are 5 years of age, as we do not have an age-appropriate scale available.

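### The SAICA is given from age 5 as a measure of treatment impact, although the protocol states its range as 6 to 18 years, and no rule covers the 5-year-olds

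*Combined protocol and SAP*

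**What the plan says.** The SAICA entry in section 8 (Assessments, item 4) says that the instrument "measures social functioning in children 6 to 18 years old". On timing and purpose it adds: "We will administer this scale at beginning of study and endpoint to assess the impact of treatment on social functioning". On scoring: "A total score is then calculated as the arithmetic mean of all global rating scores".

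The first inclusion criterion (section 6.A) reads "Male or female subjects, 5-12 years of age". Under Screening Visit, the procedures for appropriate patients include the item "An assessment battery (CBCL, SAICA, FES", with no age condition on the SAICA. Table 1 marks the SAICA at screening and at visit 12, with no footnote or substitute.

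Age 5 is dealt with elsewhere. Under Screening Visit: "The KBIT-2 will be used in the place of the WISC-IV to assess IQ in children younger than 6 years". Section 8, item 8 assigns WPPSI-III subtests for processing speed at age 5, and then says: "The working memory scale will be omitted for subjects who are 5 years of age, as we do not have an age-appropriate scale available".

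**The concern.** The protocol's own description of the instrument leaves out the youngest year of the enrolled population, yet its schedule includes that year. This looks like an oversight, since the authors checked age-appropriateness for the cognitive battery and wrote age-5 provisions there.

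The SAICA also has a different role from the two scales listed with it at screening. The CBCL and FES are given once, to characterise the groups. The SAICA is repeated at endpoint to assess treatment. Two things are at stake: whether scores from 5-year-olds mean the same as scores from older children, and whether a social-functioning result can be stated for the whole enrolled age range.

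**Working it through.** **Step 1. Compare the stated ranges.**

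| Instrument | Range or rule in the protocol | Covers age 5? |
|---|---|---|
| CBCL | 4 to 18 | Yes |
| IQ test | KBIT-2 at age 5, WASI at 6 to 12 | Yes, by substitution |
| Processing speed | WPPSI-III at age 5, WISC-IV at 6 to 12 | Yes, by substitution |
| Working memory | Omitted at age 5 | Not given |
| SAICA | 6 to 18 | No, but given |

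Eligible ages are 5 to 12. Among the instruments compared here, the SAICA is the only one given at age 5 against its stated range.

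**Step 2. Count the children affected at screening.** The documents give no expected age distribution, so there is no figure to reproduce and the share aged 5 has to be assumed. The inputs are 90 children randomised 1:1:1, 30 per arm (section 9.A). Count = share × 90; per arm = share × 30.

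| Assumed share aged 5 | Of 90 | Per arm |
|---|---|---|
| 2% | 1.8 | 0.6 |
| 5% | 4.5 | 1.5 |
| 8% | 7.2 | 2.4 |
| 12.5% (even spread: 1 of 8 single-year ages) | 11.25 | 3.75 |
| 20% | 18.0 | 6.0 |

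At 12.5%, the binomial 95% range is 6 to 18 children. Even at 2%, the chance that at least one 5-year-old enters is 1 − 0.98^90 = 0.84.

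**Step 3. Count those still aged 5 at endpoint.** Treatment lasts 12 weeks, and the study up to 15 weeks with screening (section 3). With evenly spread birthdays, 12/52 = 23% to 15/52 = 29% of children aged 5 at screening turn 6 by visit 12. Under the even-age assumption:

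- 12 weeks: 0.125 × (1 − 12/52) = 9.6%, and 90 × 0.096 = 8.7 children.
- 15 weeks: 0.125 × (1 − 15/52) = 8.9%, and 90 × 0.089 = 8.0 children.

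So 8 to 9 children would still be below the range at endpoint, against about 11 at screening.

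**Step 4. Look for a rule in the analysis plan.** Section 9 names ratings of mania and bipolar symptoms, side effects and exploratory cognition, with YMRS and CDRS in the power statement. It specifies no SAICA analysis, so nothing there sets aside or qualifies scores from age 5.

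**Step 5. Count who would remain under an age-6 limit.** 90 − 11.25 = 78.75, about 79 under even enrolment. Over the assumed range: 90 − 18 = 72 to 90 − 1.8 = 88.2, about 88.

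**The case against.** The case for leaving this alone has real substance.

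- **The measure is minor.** The primary measures are YMRS and CDRS. The SAICA is not in the list of secondary measures under Efficacy Measures, and no aim or hypothesis concerns social functioning. The GAF, PQ-LES-Q and SRS bear on neighbouring ground. All of this stands, and it limits the weight of the point.
- **The number of 5-year-olds may be small.** Children must be able to swallow pills, and those who cannot swallow the omega-3 or placebo capsules are removed (section 7, Dosing). This stands, and is why the range above starts at 2%.
- **A parent can answer.** The SAICA is a semi-structured interview of child or parent, so the comparison with performance tests given to the child is imperfect. How it behaves one year below its range cannot be judged from these documents. That is fair, but the protocol does not offer it as a justification.

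A reader might also infer more than the text supports:

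- **That out-of-range scores are pooled into one change score and weaken a planned arm comparison.** The stated mean is taken within a child, over that child's global ratings. No SAICA change score or comparison is specified.
- **That an eighth of all SAICA scores are out of range.** That share assumes equal enrolment by year of age and, even then, fits screening only.
- **That the academic component is missing or guessed at age 5.** The content does include academic performance, but the documents do not say how a child outside formal schooling is rated, or that 5-year-olds lack schooling.
- **That the arms are biased.** Randomisation is blocked to equalise age, so 5-year-olds should be spread across arms.

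**Conclusion.** The point holds as an internal mismatch: the stated range is 6 to 18, administration starts at age 5, and no provision is made although one exists for the cognitive tests. On an assumed 2% to 20% share aged 5, about 2 to 18 of 90 children fall below the range at screening. The figures of about 11 at screening and 8 to 9 at endpoint rest on even enrolment by age and evenly spread birthdays, neither of which the documents establish.

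The consequence is reduced validity and added noise in one supportive measure; the size of that noise cannot be estimated from the documents. The primary results are unaffected. The firmest consequence concerns reporting: a SAICA result given for ages 5 to 12 would claim more than the instrument's stated range allows. This is an inexpensive improvement, not a flaw that threatens the trial.

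**What to change.** In the SAICA entry of section 8, in the Screening Visit list and in a footnote to Table 1, state that the SAICA is given only to children aged 6 or over at screening. Report any SAICA result as applying to ages 6 to 12. Fixing eligibility by age at screening means that a child who turns 6 during the trial does not have an endpoint score without a starting one.

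This follows the working-memory provision as far as administration goes. That provision sets no analysis or reporting rule, so the reporting statement has to be added. If the sponsor prefers to keep 5-year-olds on the SAICA, a written justification and a sensitivity analysis without them would also close the gap.

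The cost is three short text changes and somewhat fewer children on this one measure, by the counts in step 5. The families of the youngest children would have one interview fewer at each of the two visits.
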